8.5 Unanticipated Problem Involving Risk to Subject or Other (UPIRSO)

The investigator and his or her team will follow the CHW IRB policies related to unanticipated problems involving risks to subjects or others.

8.6 Time Period and Grade of AE Capture

The period of AE capture will include from the beginning of any study procedures through 30 days following the end of the study treatment OR occur after the start of a new, non-protocol therapy (whichever occurs first) until patient meets Off Study criteria.

The criteria for grading toxicities and criteria for dose modifications will be according to CTCAE (Version 5.0).

8.7 Monitoring and Recording an Adverse Event

8.7.1 Reporting Source: AEs may be spontaneously reported by the patient and/or in response to an open question from study personnel or revealed by observation, physical examination or other diagnostic procedures.

8.7.2 Prior to the Trial: Planned hospital admissions or surgical procedures for an illness or disease that existed before the patient was enrolled in the trial are not to be considered AEs unless the condition deteriorated in an unexpected manner during the trial (e.g., surgery was performed earlier or later than planned).

8.7.3 Pretreatment Events Following Signed Informed Consent: For serious pretreatment events, the investigator must determine both the intensity of the event and the relationship of the event to study procedures.

8.7.4 Treatment Events: For serious AEs, the investigator must determine both the intensity of the event and the relationship of the event to study drug administration.

8.7.5 Not Serious AEs: For non-serious AEs, the investigator must determine both the intensity of the event and the relationship of the event to study drug administration.

8.8 Follow-Up of Adverse Events

All adverse events will be followed with appropriate medical management 30 days following the last dose of the study drug or treatment or until they are resolved, if they are related to the study treatment.

8.9 Subject Complaints

If a complaint is received by anyone on the study staff, it will be discussed with the study staff and will be addressed on a case-by-case basis. The PI will be notified of any complaints. Complaints will be reported to the IRB if indicated.

If the subject has questions about his or her rights as a study subject, wants to report any problems or complaints, obtain information about the study or offer input, the subject can contact the Children's Hospital of Wisconsin Institutional Review Board (CHW IRB), whose purpose is to see that the rights and welfare of research participants are adequately protected, and that risks are balanced by potential benefits. A member of this committee is available to speak to you if you have any questions or complaints at [contact]. This information is provided to the subject in their consent.

A product complaint is a verbal, written or electronic expression that implies dissatisfaction regarding the identity, strength, purity, quality or stability of a drug product. Individuals who identify a potential product complaint situation should immediately contact the sponsor and report the event. Whenever possible, the associated product should be maintained in accordance with the label instructions pending further guidance from a sponsor representative. Product complaints in and of themselves are not Reportable Events. If a product complaint results in an SAE, an SAE form should be completed.

8.10 Routine Reporting Procedures for AEs

Reporting to CHW Institutional Review Board

The principal investigator must report events to the CHW IRB within five business days of his/her awareness of the event.

Reporting to Amgen

All Suspected Unexpected Serious Adverse Reactions (SUSARs) are to be reported to Amgen within 24 hours of reporting to a regulatory authority. A line-listing of SAEs needs to be provided to Amgen safety every 6 months.

Please see the table below which outlines reporting information.

Event Type	Report Recipients				
	PI/Study Chair/ Coordinating Center	Institutional Review Board	DSMC	CTO Regulatory Office	Other
Serious Adverse Event	ASAP	5 days (or annual CPR)	5 days	ASAP	
Unanticipated Problems Involving Risks to Subjects of Others	ASAP	5 days (or annual CPR)	5 days	ASAP	
Evidence of Causal Relationship between Drug and AE	ASAP	5 days (or annual CPR)	5 days	ASAP	

Event Type	Report Recipients				
	PI/Study Chair/ Coordinating Center	Institutional Review Board	DSMC	CTO Regulatory Office	Other
Dose-Limiting Toxicity	ASAP	5 days (or annual CPR)	5 days	ASAP	

CPR, continuing progress report

9.0 REPORTING AND DOCUMENTING RESULTS (MEASUREMENT OF EFFECT)

Adverse Event information and reporting is in Section 8.

9.1 Evaluation of Efficacy (or Activity)

9.1.1 Definitions

Evaluable for Toxicity: All patients will be evaluable for toxicity from the time of their first exposure to Blinatumomab.

Evaluable for Objective Response: Only those subjects who have measurable disease present at baseline, have received at least one therapy cycle and have had their disease re-evaluated will be considered evaluable for response. These subjects will have their response classified according to the definitions stated below. (Note: Subjects who exhibit objective disease progression prior to the end of Cycle 1 will also be considered evaluable.)

9.2 Bone Marrow Response Criteria

Complete Remission, MRD Negative (CR MRD)

- A bone marrow with < 5% blasts by morphology (hematologic complete remission);
AND
- MRD < 0.01% by flow;
AND
- No evidence of circulating blasts or extramedullary disease;
AND
- Recovery of peripheral counts (ANC > 500/ μ L and PLT count > 50,000 μ L).
- Qualifying marrow and peripheral counts should be performed within 1 week of each other

Complete Remission (CR)

- A bone marrow with < 5% blasts by morphology (hematologic complete remission);
AND
- No evidence of circulating blasts or extramedullary disease;
AND
- Recovery of peripheral counts (ANC > 500/ μ L and PLT count > 50,000 μ L).
- Qualifying marrow and peripheral counts should be performed within 1 week of each other.

Complete Response with Incomplete Count Recovery (CRi)

- A bone marrow with < 5% blasts by morphology (hematologic complete remission); **AND**
- No evidence of circulating blasts or extramedullary disease; **AND**
- Insufficient recovery of absolute neutrophil counts (ANC < 500/ μ L), and or insufficient recovery of platelets (PLT counts < 50,000/ μ l),

Partial Remission (PR)

- Complete disappearance of circulating blasts and one of the following:
- A decrease of at least 50% of blasts in the bone marrow with > 5% and \leq 20% blasts by morphology with recovery of peripheral counts (ANC > 500/ μ L and PLT count > 50,000 μ L)

Note: only patients who entered the study with \geq 20% blasts in the marrow may be assessed as PR

Stable Disease (SD)

Patient does not satisfy the criterion for either CR, CRi, PR or disease progression.

Progressive Disease (PD)

An increase of at least 25% in the absolute number of bone marrow or circulating leukemic cells, development of new sites of extramedullary disease, or other laboratory or clinical evidence of progression of disease.

Not Evaluable (NE)

Aplastic or severely hypoplastic marrow without any blast percentage. Bone marrow aplasia/hypoplasia is defined as overall marrow cellularity less than 10-20%. In this instance, marrow evaluation should be repeated every 1-2 weeks until response determination can be made.

Relapse

After documentation of remission, one bone marrow aspirate and/or biopsy showing \geq 5% leukemic blasts or pathological evidence of extramedullary disease.

9.3 Evaluation of Safety

Analyses will be performed for all patients having received at least one dose of study drug. The study will use the CTCAE (Version 5.0) for reporting of nonhematologic adverse events and modified criteria for hematologic adverse events. See Section 8.

10.0 STATISTICAL CONSIDERATIONS

10.1 Study Endpoints/Efficacy Variables

10.1.1 Primary Efficacy Variables

The primary efficacy variable is the percent of subjects that remain in Complete Remission (CR) and become Flow Cytometry-MRD negative (FC-MRD negative) $< 0.01\%$ (Flow Cytometry performed at the University of Washington, [name] or local lab if applicable) after completion of 1 or 2 cycles of blinatumomab.

10.1.2 Secondary Efficacy Variables

- The percent of subjects that remain in CR, achieve MRD negative by Flow Cytometry ($< 0.01\%$) and by molecular High-Throughput Deep Sequencing (HTS-MRD negative) (MRD undetectable) (Adaptive Technologies, Seattle, WA) after completion of 1 to 2 cycles of Blinatumomab.

10.2 Study Design

This is an open label non-blinded Phase 2 study of up to 35 children, adolescent and young adults with B-ALL and MRD $\geq 0.01\%$. The study will continue until there are at least 25 evaluable subjects who are FC-MRD negative ($< 0.01\%$) or 35 subjects are recruited.

10.3 Determination of Sample Size and Accrual Rate

10.3.1 Sample Size and Power Estimate

Blinatumomab has been evaluated in children with relapsed/refractory B-ALL. Among the 70 pediatric patients who received the recommended dosage, 27 (39%; 95% CI, 27% to 51%) achieved complete remission (CR) within the first two cycles, 14 (52% of 70 or 20% overall) of whom achieved complete MRD negative response. If we were to receive this response our 95% CI would be 9.8%, with 35 patients. In our patients who will be in a complete remission ($< 5\%$ blasts) at the time of receiving blinatumomab, we expect a higher response rate than what was reported in the pediatric trial for relapse/refractory patients. For 35 subjects, with the widest margin for a one-sided CI of 0.15 when the proportion is 0.5 we will have a reasonable estimate.

It is expected that the study will complete recruitment in 30 to 36 months. If there is an 80% rate of MRD negative ($< 0.01\%$) subjects, a total of 25 evaluable subjects will be recruited. The 95% confidence interval will be (0.59,0.93) for 25 patients. If we must recruit 35 total subjects, we would expect that the proportion will be no less than 0.67 with a 95% CI of (0.47,0.83).

We expect ~40% (10 patients) will be HTS-MRD negative (undetectable MRD). With 25 evaluable subjects recruited the 95% CI would be (0.21,0.61).

10.3.2 Accrual Estimates

We expect to have 8-10 eligible subjects per year with about 6 to 8 consenting per year. Thus, the time to accrual will be 30 to 36 months.

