5.5.5 Withdrawal Documentation Procedure

The reason for study withdrawal and the date the subject was removed from the study must be documented in the case report form (CRF). As this study will enroll up to 35 patients in order to capture 25 evaluable subjects, it will account for subjects that may withdraw from study. Any subject who receives any amount of blinatumomab will be evaluable for toxicity and followed until they either come off study or begin a new treatment for their leukemia, which would include HCT.

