10.4 Interim Analyses, Missing Data and Stopping Rules

A planned interim analysis will be performed upon enrolling 12 evaluable subjects. Using a Fleming 2-stage design with a target accrual goal of 25 subjects, our null hypothesis is that the response rate is less than or equal to 0.400 versus the alternative that it is greater. Success for this study will be a response rate of at least 67% MRD negativity (< 0.01%). At the first stage we have 12 evaluable subjects and the cumulative number of successes, R , will be compared to the acceptance value and rejection value numbers for that stage. If $R \leq 4$, the study committee will reevaluate the study and determine if changes to the protocol design are necessary. If $R \geq 10$, then there is a very high chance of success. Similarly, after 25 evaluable subjects are recruited, if $R < 15$ we would not have met our 60% threshold. The type I error rate would be 0.0333. The power, calculated at a response rate of 0.670, is 0.8071. The calculation is done using PASS 15.

Missing Data: The dropout pattern will be plotted and summarized. Subjects who dropout before the first cycle of blinatumomab is completed will not have an MRD assessment. Subjects that are not MRD negative ($\geq 0.01\%$) at the end of the first cycle, proceed to a second cycle of blinatumomab, but dropout before the second cycle is completed will not have a final MRD assessment. Our primary outcome is the number of subjects who can achieve FC-MRD negativity (< 0.01%) after one or two cycles of blinatumomab. Hence the primary assessment is the proportion of subjects achieving FC-MRD negativity and completing these treatments.

However, secondary outcomes will include:

- The proportion of subjects achieving FC-MRD negativity (< 0.01%) after completing the first cycle of blinatumomab.
- The proportion of subjects achieving HTS-MRD negativity (MRD undetectable) after completing the first cycle of blinatumomab.
- The proportion of subjects achieving FC-MRD negativity (< 0.01%) out of all subjects recruited.
- The proportion of subjects achieving HTS-MRD negativity (MRD undetectable) out of all subjects recruited.

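### The stated consent rate does not give 25 subjects in 30 to 36 months, and the 95% CI attached to 35 subjects has an unstated denominator (minor)

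*Combined protocol and SAP*

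**What the plan says.** On accrual, section 10.3.2 gives the rate, "We expect to have 8-10 eligible subjects per year with about 6 to 8 consenting per year", and draws the duration from it: "Thus, the time to accrual will be 30 to 36 months". Section 10.3.1 repeats the period ("It is expected that the study will complete recruitment in 30 to 36 months"), as do section 3.3 and two entries of the Protocol Summary. Section 3.4 puts study completion at 42 to 48 months. The number to be reached is 25 in section 10.4 ("Using a Fleming 2-stage design with a target accrual goal of 25 subjects") and in section 10.3.1, at an 80% MRD-negative rate ("a total of 25 evaluable subjects will be recruited").

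On precision, section 10.3.1 and the Protocol Summary give three 95% intervals: (0.59,0.93) for 80% of 25, (0.21,0.61) for 10 of 25, and one for the case where 35 subjects in total have to be recruited: "we would expect that the proportion will be no less than 0.67 with a 95% CI of (0.47,0.83"). The only pairing of 35 with an evaluable count is in section 5.5.5: "As this study will enroll up to 35 patients in order to capture 25 evaluable subjects".

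**The concern.** Section 10.3.2 presents the duration as a consequence of the rate, so the two should agree by simple multiplication. They do not. Sections 3.3 and 3.4, section 10.3.1 and the Protocol Summary all depend on the same period, so a reader planning drug supply, staffing or monitoring would work to a timeline that the stated rate does not support.

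The interval raises a smaller question. A proportion of 0.67 with 35 subjects does not give the printed limits, so the reader cannot tell which sample size that precision statement describes.

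**Working it through.** **Accrual**

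Inputs: 6 to 8 consents a year (10.3.2); 30 to 36 months, that is 2.5 to 3 years (10.3.2); goal of 25 (10.4). The rate is read as study-wide, and every consenting subject is counted as evaluable, which favours the plan.

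Subjects accrued = rate × years. Months to 25 = 25 / rate × 12.

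| Consents per year | By month 30 | By month 36 | Months to reach 25 |
|---|---|---|---|
| 6 | 6 × 2.5 = 15 | 6 × 3 = 18 | 50 |
| 7 | 17.5 | 21 | 42.9 |
| 8 | 8 × 2.5 = 20 | 8 × 3 = 24 | 37.5 |

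The plan's period is not reproduced: no cell reaches 25 by month 36. The shortfall beyond month 36 runs from 37.5 − 36 = 1.5 months to 50 − 36 = 14 months.

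Working backwards, 25 subjects in 36 months needs 25 / 3 = 8.3 consents a year, and in 30 months 25 / 2.5 = 10 a year. That is close to the 8 to 10 *eligible* subjects in the same sentence (10 a year gives 25 at month 30; 8 a year gives 24 at month 36).

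Knock-on for section 3.4: the present gap between 3.3 and 3.4 is 42 − 30 = 48 − 36 = 12 months. Keeping it gives 37.5 + 12 = 49.5 to 50 + 12 = 62 months.

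**Interval**

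Method: exact (Clopper-Pearson) limits for x successes out of n. The lower limit is the 2.5% quantile of Beta(x, n − x + 1) and the upper limit is the 97.5% quantile of Beta(x + 1, n − x).

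The section's other two intervals reproduce, which identifies the method:

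- 20/25: (0.593, 0.932), printed (0.59,0.93).
- 10/25: (0.211, 0.613), printed (0.21,0.61).

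The third, by the same method:

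- 20/30 = 0.667: (0.472, 0.827), which rounds to the printed (0.47,0.83).
- 23/35 = 0.657: (0.478, 0.809).
- 24/35 = 0.686: (0.507, 0.831).

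Since 0.67 × 35 = 23.45, 23 and 24 are the counts nearest 0.67, and neither gives the printed limits. Among all x/n with n from 10 to 100, only 20/30 gives an exact interval that rounds to (0.47,0.83). No x/35 matches under Wald, Wilson, Agresti-Coull or Jeffreys limits either. For n from 15 to 40, the one other match under any of these methods is Jeffreys for 16/24, but Jeffreys gives (0.616, 0.919) for 20/25 and so does not fit the rest of the section.

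The plan says 0.67 is a floor. With n = 35, 23/35 falls below it, so 24/35 with (0.51,0.83) is the smallest count that meets it.

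**The case against.** *The inputs are approximate.* The plan hedges both the expectation and the rate, and at 8 a year for 36 months it is one subject short. That stands for the favourable corner. It does not cover the rest of the range: the midpoint of 7 a year needs 42.9 months.

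*The rate may be per site.* The Protocol Summary lists two sites. At 12 to 16 a year the count would be 12 × 2.5 = 30 to 16 × 3 = 48, and the conflict would disappear. Section 10.3.2 has no per-site qualifier, so the study-wide reading is the natural one. If per site was meant, the text should say so.

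*The interval is probably right.* Section 10.4 says that early dropouts have no MRD assessment, and section 10.6 limits the primary efficacy group to subjects with one. A denominator below the number recruited is therefore what the plan implies, and 20/30 fits the 0.67. This largely stands. A reader might infer that the interval was miscalculated, but the documents do not support that. What remains is a missing label. It still matters to the reader because section 5.5.5 pairs 35 enrolled with 25 evaluable, not 30, and sections 10.4 and 10.6 also plan results over all subjects recruited, where the denominator would be 35.

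*The gap could be far larger.* Section 10.2 says "The study will continue until there are at least 25 evaluable subjects who are FC-MRD negative", with 35 recruited as the alternative end point. A reader might infer a much longer timeline from a count of responders or from the cap of 35. Which target the timeline serves is not settled in the documents, so the shortfall here is measured only against 25 evaluable subjects, the reading kindest to the plan.

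**Conclusion.** The accrual statement does not follow from its own input. At 6 to 8 study-wide consents a year, 25 subjects take 37.5 to 50 months, against a stated 30 to 36. The excess over month 36 is 1.5 to 14 months. This assumes a constant study-wide rate and that every consenting subject is evaluable; any loss lengthens it.

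The interval is, most likely, a correct exact interval for 20/30 attached to 35 recruited subjects without its denominator. Against 24/35 the lower limit differs by 0.04 and the rounded upper limit is the same.

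Both are minor. A reader might infer that the trial would stop short of its sample size or lose power. The documents do not support this: section 10.2 ends enrolment by count, not by date, and no decision rule uses the interval. The boundary of 15 out of 25, the type I error and the power are unaffected. Nor do the documents show that the duration was computed from the eligible rate instead of the consent rate; the near match in the arithmetic is suggestive only.

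**What to change.** 1. Make rate and duration agree in the Protocol Summary and in sections 3.3, 3.4, 10.3.1 and 10.3.2, and say which target the timeline serves. Either restate enrolment as about 38 to 50 months for 25 evaluable subjects and move section 3.4 to match (about 50 to 62 months if the 12-month gap is kept), or, if the rate is misstated, correct it: 25 subjects in 30 to 36 months needs 8.3 to 10 consents a year. If the rate is per site, say so.
2. In section 10.3.1 and the Protocol Summary, either state that (0.47,0.83) assumes 30 evaluable of 35 recruited (20/30), or, if the denominator is 35, give 24/35 = 0.69 with (0.51,0.83).

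The cost is protocol wording only, with no added patients or procedures. If the consent rate is kept, the stated timeline becomes longer.

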10.4 Interim Analyses, Missing Data and Stopping Rules

A planned interim analysis will be performed upon enrolling 12 evaluable subjects. Using a Fleming 2-stage design with a target accrual goal of 25 subjects, our null hypothesis is that the response rate is less than or equal to 0.400 versus the alternative that it is greater. Success for this study will be a response rate of at least 67% MRD negativity (< 0.01%). At the first stage we have 12 evaluable subjects and the cumulative number of successes, R , will be compared to the acceptance value and rejection value numbers for that stage. If $R \leq 4$, the study committee will reevaluate the study and determine if changes to the protocol design are necessary. If $R \geq 10$, then there is a very high chance of success. Similarly, after 25 evaluable subjects are recruited, if $R < 15$ we would not have met our 60% threshold. The type I error rate would be 0.0333. The power, calculated at a response rate of 0.670, is 0.8071. The calculation is done using PASS 15.

Missing Data: The dropout pattern will be plotted and summarized. Subjects who dropout before the first cycle of blinatumomab is completed will not have an MRD assessment. Subjects that are not MRD negative ($\geq 0.01\%$) at the end of the first cycle, proceed to a second cycle of blinatumomab, but dropout before the second cycle is completed will not have a final MRD assessment. Our primary outcome is the number of subjects who can achieve FC-MRD negativity (< 0.01%) after one or two cycles of blinatumomab. Hence the primary assessment is the proportion of subjects achieving FC-MRD negativity and completing these treatments.

However, secondary outcomes will include:

- The proportion of subjects achieving FC-MRD negativity (< 0.01%) after completing the first cycle of blinatumomab.
- The proportion of subjects achieving HTS-MRD negativity (MRD undetectable) after completing the first cycle of blinatumomab.
- The proportion of subjects achieving FC-MRD negativity (< 0.01%) out of all subjects recruited.
- The proportion of subjects achieving HTS-MRD negativity (MRD undetectable) out of all subjects recruited.

Patients who drop out or are removed from the study due to an adverse symptom profile will be reported as a safety outcome. Characteristics of these will be summarized. The occurrence of toxic death (TD) at any time during protocol therapy will be a primary endpoint for safety monitoring and a stopping rule. A population toxic death rate that exceeds $p_0=0.10$ will be considered unacceptable. Operationally, this criterion will be satisfied if the following fractions of TDs out of total patients treated are exceeded: $\geq 1/5$, $\geq 2/12$, $\geq 3/20$, $\geq 4/28$, and so on as dictated by this rule. If this criterion is satisfied at any time the cause and circumstances of these deaths will be reviewed with the study committee and with the Data and Safety Monitoring Committee to determine whether modifications to or termination of the study is warranted.

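### Section 10.4 leaves 15 or 16 responders of 25 without a conclusion, and its printed boundaries do not give the stated type I error and power

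*Combined protocol and SAP*

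**What the plan says.** All elements of the decision rule are in section 10.4. The design is introduced with "Using a Fleming 2-stage design with a target accrual goal of 25 subjects". The null is a response rate of at most 0.400, and an interim look is planned at 12 evaluable subjects.

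- **Success definition:** "Success for this study will be a response rate of at least 67% MRD negativity".
- **Stage 1, R ≤ 4 of 12:** "the study committee will reevaluate the study and determine if changes to the protocol design are necessary".
- **Stage 1, R ≥ 10 of 12:** "then there is a very high chance of success".
- **Final stage, R < 15 of 25:** "we would not have met our 60% threshold".
- **Operating characteristics:** "The type I error rate would be 0.0333. The power, calculated at a response rate of 0.670, is 0.8071".

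Two other sections bear on the rule. Section 10.3.1 uses the same figure for another purpose: if 35 subjects have to be recruited, "we would expect that the proportion will be no less than 0.67". Section 10.2 sets the end of recruitment: "The study will continue until there are at least 25 evaluable subjects who are FC-MRD negative", or until 35 are recruited. Section 10.7.2 reports the primary proportion with a 95% confidence interval and gives no decision rule.

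**The concern.** The paragraph contains two final thresholds. One defines success (67%) and the other defines failure (fewer than 15, or 60%), and they do not meet. With 15 or 16 responders the sponsor would have to decide whether the trial succeeded after seeing the result.

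The threshold also determines the power. A reader who takes the 67% sentence at its word will believe that the trial has 81% power to meet it.

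Finally, the stage-1 actions are worded as prompts for discussion and not as stops. A reader cannot tell which rule the quoted type I error and power belong to, or check them.

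**Working it through.** **Inputs (all from section 10.4).** n1 = 12 and N = 25, so n2 = 13. Null rate p0 = 0.40; power is evaluated at p1 = 0.67. Stage-1 bounds are R ≤ 4 and R ≥ 10. The final failure rule is R < 15. Stated type I error is 0.0333 and stated power 0.8071.

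**Step 1: thresholds as counts.** 0.67 × 25 = 16.75, so success needs 17 or more (17/25 = 68%). 0.60 × 25 = 15, so the failure rule ends at 14. The counts 15 (60%) and 16 (64%) fall between the two.

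**Step 2: how likely the gap is.** For a binomial count on 25 subjects:

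- p = 0.67: P(15) + P(16) = 0.1232 + 0.1564 = 0.2796
- p = 0.60: 0.1612 + 0.1511 = 0.3122
- p = 0.40: 0.0212 + 0.0088 = 0.0301 (from unrounded terms)

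If both stage-1 bounds stop the trial, only stage-1 counts of 5 to 9 continue, and the probabilities become 0.2640, 0.2955 and 0.0286.

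**Step 3: the plan's own figures.** With X1 ~ Bin(12, p), X2 ~ Bin(13, p) and final cut-off c:

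P(reject | p) = P(X1 ≥ 10) [only if the upper bound stops the trial] + Σ P(X1 = x) · P(X2 ≥ c − x), summed over the stage-1 counts x that continue.

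For c = 15 with both bounds binding:

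- p = 0.40: 0.00281 + 0.03221 = 0.03502
- p = 0.67: 0.18756 + 0.64279 = 0.83035

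All four readings of the stage-1 bounds, with c = 15:

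| Stage-1 bounds that stop the trial | Type I error | Power at 0.67 |
|---|---|---|
| Both | 0.0350 | 0.8303 |
| Lower only | 0.0341 | 0.8292 |
| Upper only | 0.0353 | 0.8325 |
| Neither | 0.0344 | 0.8314 |
| **Stated** | **0.0333** | **0.8071** |

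No reading gives either stated figure. Type I error exceeds the stated value by 0.0008 to 0.0020, and power exceeds it by 0.022 to 0.025.

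**Step 4: which cut-off the stated figures fit.**

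| Final cut-off | Type I error, both / neither binding | Power at 0.67, both / neither binding |
|---|---|---|
| 15 | 0.0350 / 0.0344 | 0.8303 / 0.8314 |
| 16 | 0.0147 / 0.0132 | 0.7122 / 0.7081 |
| 17 | 0.0064 / 0.0043 | 0.5663 / 0.5518 |

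The stated values lie close to the row for 15 and far from the row for 17.

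**Step 5: a search for the source.** All stage-1 bounds at 12 subjects were tried with final cut-offs from 12 to 18 of 25. Only one set gives 0.0333: R ≤ 5, R ≥ 10, R ≥ 15 (0.03325). Its power is 0.8152, not 0.8071. No set gives 0.8071.

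**Step 6: more than 25 assessed.** Section 10.2 allows up to 35 subjects. On 35, 60% is 0.60 × 35 = 21 and 67% is 23.45, so 24. A count of 15 would be only 15/35 = 43%.

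**The case against.** The strongest reply is that the test itself is determinate. A Fleming design compares the count with an acceptance and a rejection number at each stage. If R < 15 is the acceptance side at 25 subjects, then 15 or 16 rejects the null. On this view 67% is the target rate used for power, loosely worded, and 17 of 25 is a count that the plan never prints. The stated error rates, which fit 15, support this.

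That reading is plausible and may be what was intended. It does not remove the conflict: the sentence calls 67% the criterion for success, and a separate sentence already names 0.670 as the rate for power.

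A second reply is that this is a single-arm phase 2 trial whose primary result is a proportion with a confidence interval, reported whatever the count. That is true and limits the harm to the success claim. But section 10.4 is the only place where that claim is defined.

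A third reply is that the mismatch in type I error and power is trivial and probably a transcription slip. With R ≤ 5 at stage 1 the type I error matches, and an alternative of 0.667 would give power 0.8066, close to the stated value. The gap is indeed small, and this explanation is possible, but the documents do not confirm it.

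A fourth reply is that the final rule refers to 25 evaluable subjects, so 35 is outside it. That is correct, and for that reason the plan must say what happens if more than 25 are assessed. Section 10.2 also counts subjects who are already MRD negative, and fixing the cut-off alone does not reconcile that with the denominator of 25.

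**Conclusion.** The concern holds. As written, section 10.4 gives no conclusion for 15 or 16 responders of 25, a result with probability 0.28 at a true rate of 0.67 and 0.31 at 0.60 (0.26 and 0.30 if the stage-1 bounds stop the trial). The stated power of 0.8071 does not apply to the 67% success definition, under which power at 0.67 is 0.55 to 0.57 and type I error 0.004 to 0.006.

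The second part, that the printed boundaries do not reproduce the stated type I error and power, also holds under all four readings of the stage-1 bounds. It is a reporting error of small size and does not show an inflated or underpowered design.

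The calculations assume independent binomial responses, exactly 12 and 25 assessed subjects, and 67% read as an observed rate. Because the first part affects the only success rule for the primary endpoint, it must be corrected before outcomes are known.

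**What to change.** 1. **State one final cut-off** in section 10.4 and say that any lower count is not a success. If the quoted error rates are to stand approximately, the cut-off is R ≥ 15 of 25, and 0.67 should be labelled as the alternative used for power. If 17 of 25 is meant, change the final-stage sentence to R < 17 and restate power at 0.67 as 0.55 (stage-1 bounds not binding) or 0.57 (both binding). The sponsor must say which governs.
2. **Check the PASS output**, say for each stage-1 bound whether it stops the trial, and restate boundaries, type I error and power together. For the printed bounds with a cut-off of 15 these are 0.0350 and 0.830 if both bind, or 0.0344 and 0.831 if neither does. R ≤ 5 should not be substituted at stage 1 unless that output supports it.
3. **Say which subjects the rule counts:** the first 25 assessed, or a stated cut-off for larger numbers, with a cross-reference in section 10.2.

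The cost is a few sentences in section 10.4, one cross-reference in section 10.2 and a check of the software output. The sample size does not change.
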